10.4.3 Analysis of the Secondary Endpoints

For the phase I portion of the study data will be obtained on ORR, duration of response, PFS, OS, and ratio of participants that are hospitalized because of adverse events attributed to disease progression.

10.4.4 Duration of Response

The duration of overall response is measured from the time measurement criteria are met for CR or PR (whichever is first recorded) until the first date that PD is objectively documented and is evaluated using the Kaplan-Meier method.

10.4.4.1 Progression-Free Survival and Relapse-Free survival

PFS and RFS will be evaluated using Kaplan-Meier methods. PFS will be defined as the time from the date of first treatment to the date of disease progression or death (any cause) whichever occurs first. RFS will be defined as the time from completion of standard chemoradiation to the date of disease recurrence or death (any cause) whichever occurs first. Subjects who do not have disease progression, disease recurrence or have not died at the end of follow up will be censored at the last known date the subject was progression or relapse free.

10.4.4.2 Objective Response

Objective response is a complete or partial radiographic response as defined by RECIST 1.1 (Section [6.3.5](#)).

10.4.4.3 Overall Survival

OS will be evaluated using Kaplan-Meier methods. OS will be defined as the time from the date of first treatment to the date of death (any cause). Subjects who are alive at the end of follow up will be censored at the last known date alive.

10.4.5 Safety Analyses

Safety endpoints will be analyzed as summary statistics during treatment and/or as change scores from baseline assessments. AEs will be coded as defined in the Medical Dictionary for Regulatory Activities (MedDRA). All AEs will be recorded and tabulated following each treatment. AEs will be recorded by severity, frequency, and relationship to the study intervention and will be presented by System Organ Class (SOC) designations and preferred term groupings. Information on each AE will include start date, stop date, severity, relationship, expectedness, outcome, and duration. Adverse events leading to premature discontinuation from the study intervention and serious treatment-emergent AEs will be presented either in a Table or a Listing.

In addition, overall safety will be assessed by descriptive analyses using tabulated frequencies of AEs by grade using CTCAE Version 5 within dose cohorts and for the overall study population in terms of treatment-emergent AEs, SAEs, and clinically significant changes in safety laboratory tests, physical examinations, ECGs, and vital signs.

10.4.6 Baseline Descriptive Statistics

Baseline Characteristics will be described.

10.4.7 Planned Interim Analyses

Interim assessment of safety will be made based on DLT assessments according to the 3+3 dose escalation design in the phase I portion of the study and the first six participants enrolled on the phase II portion of the study.

10.4.8 Tabulation of Individual Participant Data

Individual responses in a cohort may be depicted within a larger group using a waterfall plot or spider diagram.

10.4.9 Exploratory Analyses (Immune Responses)

Where feasible, exploratory immune analyses will be conducted to evaluate anti-tumor immune responses. Immune response will be assessed among all subjects treated in each cohort. The

magnitude of immune responses will be described. A subject will be considered evaluable for immune response if they receive at least one dose of treatment. The percentage of subjects with a positive immune response will be evaluated by cohort. For flow cytometry analyses on PBMC samples, Student T tests or Kruskal-Wallis and Wilcoxon rank sum tests as appropriate will be performed on percentages of TNF- α and/or IFN- γ expressing cells among the different cohorts to determine any significant differences in cell populations. For antigen specific T cell responses, a positive immune response is defined by CMI reactivity in *ex vivo* stimulation using a flow cytometric readout (cytokine production or CD107 expression). Antigen-specific peptide challenge assays require a readout of >250 reactive T-cells/million cells above the background (53).

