6. Participants who have completed neoadjuvant or induction immunotherapy on the phase II portion of the protocol will be followed by phone or email for recurrence, adverse events and survival starting 2 months (+/- 2 weeks) after safety visit and then annually (+/- 1 month) until the patient is 5 years out from surgery or completion of chemoradiotherapy.

7. As indicated in Section **12.3**, all subjects will be offered the opportunity to complete an NIH advanced directive form. This should be done preferably at baseline but can be done at any time during the study as long as the capacity to do so is retained. The completion of the form is strongly recommended but is not required.

8. Biochemical profile: Acute care, hepatic and mineral panel as described in Sections **2.2** and **2.4**.

9. In HIV positive participants.

10. Imaging (CT of neck and chest/ MRI, if indicated, for oropharyngeal cancer participants; CT of skull, neck and chest/ MRI, if indicated, for sinonasal SCC; no CT chest required if PET/CT available) at baseline/screening, and at Week 4-5 (CT of neck/ MRI, if indicated, for oropharyngeal cancer participants; CT of skull, neck/ MRI, if indicated, for sinonasal SCC). MRI (with gadolinium) will be used when CT scan is not an option to follow the disease. Bone scans and other imaging assessments may also be performed as clinically indicated. Post-treatment imaging is to be strongly pursued but is not required and may be waived at the discretion of the PI.

11. Where feasible, biopsies will be done at baseline as well as at week 4-5. Biopsies will be done by ENT under direct visualization. Where feasible at least 2 cores will be obtained. If a recent (\leq 6 months preferred) outside biopsy has been performed that specimen may be used in lieu of a baseline biopsy. For patients that have surgery as definitive treatment, Week 4-5 biopsy may be omitted: in this case tumor biospecimens will be obtained from the institution where the patient underwent surgery after the patient signs that institution's release document.

12. Where feasible, research blood (see Section **5.1**) will be collected at baseline, week 3 and week 45 with the following exceptions:

- Samples for AVA analysis will be taken prior to infusion on W1, W3, with research labs on 4-5 or with end of treatment labs if participants come off treatment prior to any of those timepoints.
- Note: Samples may be sent to Precigen, Inc for additional analyses (see Section **5.1.9**).

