5.1.1 Immune Phenotyping

Exploratory immunologic studies will be conducted to evaluate the study drug's effect on the immune response before and after treatment, to gain insight into potential biomarkers, and help improve the administered therapy. Blood will be collected as per the **Study Calendar**. The following immune assays may be performed at the Laboratory of Tumor Immunology and Biology (LTIB) at the NCI's Center for Cancer Research (CCR) in select participants where adequate samples are available:

1. PBMCs may be analyzed for changes in standard immune cell types (CD4 and CD8 T cells, natural killer [NK] cells, regulatory T cells [Tregs], myeloid-derived suppressor cells

[MDSCs], and dendritic cells) as well as 123 immune cell subsets, using multi-color flow cytometry.

2. PBMCs from selected subjects may be analyzed for function of specific immune cell subsets, including CD4 and CD8 T cells, NK cells, Tregs, and MDSCs using flow-based assays.
3. PBMCs may be analyzed for tumor antigen-specific immune responses using an intracellular cytokine staining assay. PBMCs will be stimulated in vitro with overlapping 15-mer peptide pools encoding the tumor-associated antigens HPV 16 E6 and E7 and HPV18 E6 and E7; control peptide pools will involve the use of human leukocyte antigen peptide as a negative control and CEFT peptide mix as a positive control. CEFT is a mixture of peptides of CMV, Epstein-Barr virus, influenza, and tetanus toxin. Post-stimulation analyses of CD4 and CD8 T cells will involve the production of IFN- γ , IL-2, TNF, and the degranulation marker CD107a. If sufficient PBMCs are available, assays may also be performed for the development of T cells to other tumor-associated antigens.

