10.3 POPULATIONS FOR ANALYSES

All participants who receive any investigational treatment will be evaluable for safety and toxicity evaluations.

For phase II, only HPV-OPC participants will be evaluable for primary and secondary objective endpoints. HPV-SNSCC participants will be evaluable only for exploratory objectives.

For phase II, participants who receive at least two doses of therapy and have an adequate pretreatment and posttreatment biopsy will be evaluable for immune infiltration assessments. For phase II, participants who receive at least two doses of immunotherapy and go on to receive standard definitive therapy will be evaluable for relapse free survival and overall survival assessments.

For phase I and II participants, only those participants who have measurable disease present at baseline and have had their disease re-evaluated will be considered evaluable for response. (Note: Participants who exhibit objective disease progression prior to the end of cycle 1 will also be considered evaluable.)

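### The exploratory positive-immune-response percentage takes everyone dosed as evaluable, although only assayed participants can be positive, so on the plain reading it is a lower bound and not an estimate

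*Combined protocol and SAP*

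**What the plan says.** Section 10.4.9 makes three statements that belong together. The population is all treated subjects: "Immune response will be assessed among all subjects treated in each cohort". Evaluability is set by dosing alone: "A subject will be considered evaluable for immune response if they receive at least one dose of treatment". The summary is a proportion: "The percentage of subjects with a positive immune response will be evaluated by cohort". The same section defines a positive antigen-specific response by a flow-cytometric readout and gives the threshold: "Antigen-specific peptide challenge assays require a readout of >250 reactive T-cells/million cells above the background".

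Section 5.1.1 describes who is assayed. The immune assays are optional and are run "in select participants where adequate samples are available". The antigen-specific assay is optional too: "PBMCs may be analyzed for tumor antigen-specific immune responses using an intracellular cytokine staining assay". The footnotes to both study calendars (3.4.1 and 3.4.2) make research blood collection conditional on feasibility.

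Section 10.3 treats other endpoints differently. For tumor infiltration in phase II, participants must have had at least two doses and must "have an adequate pretreatment and posttreatment biopsy will be evaluable for immune infiltration assessments". For RECIST response, disease must have been re-evaluated, or have progressed early. Both rules require the measurement to exist. Section 10.3 sets no rule for the blood-based immune response.

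**The concern.** The evaluable set and the set that can yield a result differ, and the plan itself anticipates the gap by making the assays selective. If the evaluable set in 10.4.9 is the denominator, a participant who was dosed but not assayed adds one to the denominator and can never add one to the numerator. The percentage then reflects two things together: how often assayed participants respond, and how many participants were assayed. A low figure could mean a weak response or thin sampling, and the figure alone would not show which.

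**Working it through.** **No plan figure to reproduce.** The documents give no expected rate, target or sample size for this percentage. The rates and assayed shares below are therefore assumptions, taken over a range.

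**Inputs from the documents.** Evaluable means at least one dose (10.4.9). Positive requires a readout above background (10.4.9). Assays are run in selected participants with adequate samples (5.1.1). The p16+ oropharyngeal cohort has 20 participants (10.2), and Arm 1B is expanded to 10 evaluable participants (10.4.1).

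**Formula.** Let N be the number dosed, m the number assayed and x the number positive.

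- Rate among assayed = x/m.
- Rate under the 10.4.9 evaluable set = x/N = (x/m) × (m/N).
- If every unassayed participant were negative, the cohort proportion would be x/N. If every one were positive, it would be (x + N − m)/N. The all-dosed figure is therefore the lower of the two bounds.

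**Illustration with an assumed 60% rate among assayed.**

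- 90% assayed: 0.60 × 0.90 = 0.54
- 75% assayed: 0.60 × 0.75 = 0.45
- 50% assayed: 0.60 × 0.50 = 0.30
- 100% assayed: 0.60 × 1.00 = 0.60, no dilution

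**At the trial's group sizes** (assumed counts; exact Clopper-Pearson 95% intervals):

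| Dosed N | Assayed m | Positive x | x/m (95% CI) | x/N (95% CI) | Bounds |
|---|---|---|---|---|---|
| 20 | 16 | 10 | 62.5% (35.4 to 84.8) | 50.0% (27.2 to 72.8) | 50% to 70% |
| 20 | 10 | 6 | 60.0% (26.2 to 87.8) | 30.0% (11.9 to 54.3) | 30% to 80% |
| 10 | 8 | 5 | 62.5% (24.5 to 91.5) | 50.0% (18.7 to 81.3) | 50% to 70% |
| 10 | 5 | 3 | 60.0% (14.7 to 94.7) | 30.0% (6.7 to 65.2) | 30% to 80% |

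The all-dosed interval is narrower only because unassayed participants are counted as known negatives. With 20 dosed, its width is 72.8 − 27.2 = 45.6 points against 84.8 − 35.4 = 49.4 when 16 are assayed, and 54.3 − 11.9 = 42.4 against 87.8 − 26.2 = 61.6 when 10 are assayed.

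**The one-dose threshold is not the fault.** Both calendars schedule a blood draw at week 3, so a participant with a single dose can have a post-dose sample. What is missing is the condition that a result exists.

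**The case against.** The strongest defense is that the denominator is inferred. Section 10.4.9 never says that unassayed participants count as non-responders. It opens by making the immune analyses conditional on feasibility. The one-dose rule could be only an exposure threshold, set against the two doses required in 10.3, with percentages taken over participants who have results. This stands in part: the dilution follows from the plain reading and not from an express instruction. But the section says response is assessed among all treated subjects, defines evaluable by dosing alone and offers no other denominator. An analyst who drops the unassayed departs from the written definition and leaves a different gap: assay is selective, and the rule for selection is only partly stated.

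A second defense is that effect sizes built on assumed coverage say nothing about this trial. That is correct. Blood draws are scheduled for everyone, and the documents give no reason to expect 50% coverage. The effect could be negligible.

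A reader might also infer stronger conclusions that the documents do not support:

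- That comparisons between cohorts are invalid. The only between-cohort tests in 10.4.9 use percentages of cytokine-expressing cells. These are per-sample values, to which unassayed participants contribute nothing. No test across cohorts is planned for the positive-response percentage.
- That this percentage is the main evidence of immunogenicity. The primary phase II immune measure is CD3+ doubling in tumor, and 10.4.9 also describes the magnitude of response.
- That a valid pre-dose assay should be required. Positivity is defined against background, and 5.1.1 provides a negative-control peptide pool. A baseline requirement would exclude participants with a valid positive post-dose result and would go beyond the stated definition.

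**Conclusion.** The concern holds as a mismatch between a stated evaluability rule and the assay plan. On the plain reading of 10.4.9, the reported percentage is the rate among assayed participants times the fraction assayed, which makes it a worst-case bound. The conclusion rests on taking the section's evaluable set as the denominator. The plan implies this and nowhere contradicts it, but does not spell it out.

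The size cannot be determined from the documents. It is zero at full coverage and grows in proportion to the unassayed share; the 60% rate and the coverage levels used here are illustrations only. The consequence is limited: the analysis is exploratory and has no stated target or decision rule. The CD3+ primary endpoint keeps its own evaluability rule and is not affected. This is a minor point that is worth correcting because the correction is cheap.

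**What to change.** In Section 10.4.9, define evaluable for the positive-response percentage as at least one dose plus at least one valid post-dose assay result. Add that the number assayed out of the number dosed will be reported for each cohort, and that the all-dosed percentage will be shown as a sensitivity figure, labeled as the lower bound. State that selection for assay is by sample adequacy and not by clinical outcome; 5.1.1 already refers to adequate samples, so this completes an existing condition.

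The rate among assayed participants represents the cohort only if being assayed is unrelated to response. Reporting coverage beside the lower bound lets the reader judge that.

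The cost is a few lines of text, with no new samples, visits or participants. The denominator becomes smaller and the interval wider: slightly at high coverage (49.4 against 45.6 points with 16 of 20 assayed), more if coverage is poor (61.6 against 42.4 with 10 of 20).

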1.2.11 Rationale and background for performing immune assays

Multiple immune assays have been developed in the LTIB to better define the mechanism(s) involved in the use of specific novel agents, as monotherapy or in combination therapies, both for preclinical and clinical studies. In addition to analyses of biopsies, analyses of the peripheral immunome can provide valuable information where multiple samples can be analyzed over the course of a given therapy vs. pre-therapy. The LTIB has now developed and employed (45-48) a flow cytometry-based assay that can analyze 123 immune cell subsets in human PBMC from one vial of processed PBMC (approximately 10^7 cells). This assay will be used in this clinical trial to detect multiple (n=32) subsets of CD4+ T cells, CD8+ T cells (n=29), Tregs (n=7), B cells (n=5), NK (n=20), NKT (n=4), DC (n=10), and MDSC (n=16) to better understand the role of each agent. We also plan to evaluate changes in TCR clonal diversity both in biopsies and the periphery. One example of where these assays have been employed involves an ongoing first-in-human trial of the NHS-IL12 tumor-targeting immunocytokine (NCT01417546). TCR diversity increased 6-14-fold in biopsies of patients with a high or intermediate IFN- γ response but were unchanged or decreased with a low IFN- γ response. These findings also correlated with TIL in biopsies. We are also currently employing NanoString analyses to identify a gene signature in biopsies and PBMC, pre- and post-treatment.

The infiltration of p16-positive HNSCC with tumor infiltrating lymphocytes (TIL) tends to be greater than that observed in p16-negative HNSCC (49), possibly related to the presence of strong viral antigens. Supporting that these TIL are active and possess anti-tumor function, greater numbers of TIL present within p16-positive HNSCCs is positively correlated with increased survival after standard anti-cancer treatment and associated with an increased type I immune profile within the tumor (20). A meta-analysis of all published papers exploring TIL infiltration into p16-positive HNSCC demonstrated a strong, significant, positive correlation (50). Thus, changes in TIL infiltration into p16-positive HNSCCs after immunotherapy will be used for the primary outcome of the phase II portion of this study.

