2.3.2 Treatment Assignment Procedures

2.3.2.1 Cohorts

Number	Name	Description
1	Cohort 1	Subjects with advanced or metastatic HPV associated malignancies (Phase I)
2	Cohort 2	Subjects with newly diagnosed p16+ oropharyngeal cancer (Phase II): Arm 2A: Stage I (T1,T2 N1)/II/III Arm 2B: Stage II/III Note: Closed, Will Not Enroll
3	Cohort 3	Subjects with newly diagnosed stage II/III/IVA/IVB HPV+ sinonasal squamous cell cancer (Phase II)

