 - Samples for ADA analysis will be taken prior to infusion on W1, W5, and W11 or with end of treatment labs if participants come off treatment prior to any of those timepoints.
- Samples for AVA analysis will be taken prior to infusion on W1, W3, W5, W11, and restaging visits or with end of treatment labs if participants come off treatment prior to any of those timepoints.
- All other blood samples
 - Baseline, Week 3, and Week 5; restaging visits per PI discretion.
- Note: Samples may be sent to Precigen, Inc for additional analyses (see Section **5.1.9**).

16. Vital signs at screening should include pulse oximetry on room air.

17. Medical history will include monitoring for signs of bleeding.

18. Skin assessment must be performed at baseline and at least every 6 weeks, starting on week 5 during treatment and at the end of treatment or at the 28 (± 7 days) day safety follow-up (if not performed in the previous 6 weeks).

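### The only tests planned for the PBMC cytokine data compare cohorts with each other, whereas the stated aim is change from before to after treatment; no paired test is named

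*Combined protocol and SAP*

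**What the plan says.** Section 10.4.9 gives the only inferential plan for the PBMC flow cytometry data: "Student T tests or Kruskal-Wallis and Wilcoxon rank sum tests as appropriate", applied to percentages of TNF-α and/or IFN-γ "expressing cells among the different cohorts to determine any significant differences in cell populations". The rest of that section is descriptive: the magnitude of response, and the percentage of subjects with a positive response by cohort. For the peptide assays, positivity is set against assay background (more than 250 reactive T cells per million above it), not against the participant's own pre-treatment value. One dose of treatment makes a subject evaluable; a baseline and post-dose pair is not required.

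The aim is stated differently elsewhere. Section 5.1.1 says the exploratory studies evaluate the drug's "effect on the immune response before and after treatment". Section 1.2.11 justifies blood assays because "multiple samples can be analyzed over the course of a given therapy vs. pre-therapy".

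Paired samples are planned, where feasible. For Phase I the calendar (3.4.1, note 15) lists "Baseline, Week 3, and Week 5; restaging visits per PI discretion". For Phase II (3.4.2, note 12) it lists baseline, week 3 and a third time printed as 45, which the calendar's column heading shows to be Week 4-5.

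Section 2.3.2.1 defines three cohorts: advanced or metastatic disease in Phase I, newly diagnosed p16+ oropharyngeal cancer in Phase II, and newly diagnosed HPV+ sinonasal cancer in Phase II. Section 10.4.5 also uses the term for dose cohorts. Section 10.4.9 does not say which it means.

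**The concern.** The question is whether a participant's T-cell responses rise after vaccination. Kruskal-Wallis and rank sum tests are for independent groups, and a Student t test among cohorts is also unpaired, so no reading of the sentence yields a before-versus-after test.

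The cohorts of section 2.3.2.1 are also poor comparators for one another. Phase I requires a prior line of systemic chemotherapy, with exceptions (2.1.1.4); Phase II enrols newly diagnosed disease. Phase I receives the vaccine on D1, D15 and D29 with four-weekly boosters, Phase II on D1 and D15 only (3.2.1). Arm 1B adds M7824. Assignment follows disease setting and sequence, not randomisation (2.3.2.3). Cohort 3 has at most 2 participants.

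Two errors are possible. A vaccine effect shared by the cohorts would go unseen. And, on one reading of the text, a difference that existed before treatment could be reported as a result.

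**Working it through.** **The plan's own power figure.** The documents give one, for the Phase II CD3+ endpoint: 80.4% for 50% versus 80%, n = 20, exact binomial, one-sided 0.05 (10.2). Requiring at least 15 of 20 successes gives exact α = 0.0207 and power 0.8042, so it reproduces. (14 of 20 would give α = 0.0577, above 0.05.) No power, effect size or α is stated for the tests in 10.4.9.

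**Inputs from the documents.** Phase I treated: 3 + 3 + 11 = 17 (14.1.2, Table 8). Phase II oropharyngeal cohort: 20 (10.2).

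**Assumed, because the documents are silent.** Two-sided α 0.05; normal data; vaccine effect 0.5 to 0.8 SD; within-person correlation ρ 0.3 to 0.6; baseline difference between cohorts 0.25 to 1 SD.

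**1. A common effect cancels.** If both cohorts gain δ, the difference in post-treatment means is (μ₁ + δ) − (μ₂ + δ) = μ₁ − μ₂. With equal baselines the test rejects at its α; simulation of 17 versus 20 gives 4% to 6%. Testing change scores between cohorts gives δ − δ = 0, and again about 5%.

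**2. Paired test on the same data.** The SD of a within-person change is √(2(1 − ρ)), so the paired t non-centrality is d√n / √(2(1 − ρ)).
- n = 20, d = 0.5, ρ = 0.3: 0.5 × 4.472 / 1.183 = 1.89; paired t power 43%, signed-rank about 41%.
- n = 20, d = 0.8, ρ = 0.6: 0.8 × 4.472 / 0.894 = 4.00; paired t power 97%, signed-rank about 95%.
- n = 10, same two corners: non-centrality 1.34 and 2.83; signed-rank about 22% and 70%.

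Signed-rank figures are simulated; repeat runs agree within about two percentage points.

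**3. No vaccine effect, but the cohorts differ at baseline** (17 versus 20, rank sum test, simulated):

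| Baseline difference | Post-treatment values compared | Changes from baseline compared |
|---|---|---|
| 0.25 SD | about 10% | about 5% |
| 0.5 SD | about 29% | about 5% |
| 1 SD | about 81% | about 5% |

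The t test on post-treatment values has non-centrality b / √(1/17 + 1/20). For b = 0.5 this is 1.52 and rejection is 31%; for b = 1 it is 3.03 and rejection is 84%.

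**4. If cohorts means the two monotherapy dose levels.** With 3 versus 3, the smallest two-sided rank sum p is 2 / C(6,3) = 2/20 = 0.10. The Student t test, also named, can fall below 0.05: under normality its power is about 46% for a 2 SD difference.

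**The case against.** The best defence is that comparing cohorts is a legitimate question in its own right. Section 1.2.11 wants the assays to clarify the role of each agent, and vaccine alone versus vaccine plus M7824 is a between-arm contrast. A test that rejects 5% of the time when both arms gain equally is behaving correctly for its own null. That stands: the fault is not that the comparison appears, but that it is the only test planned and does not address the stated before-and-after aim.

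It can also be said that change is not ignored. Section 10.4.9 describes the magnitude of response, and sections 5.1.1 and 5.1.2 allow samples to be analysed for changes. A reader might therefore go too far in concluding that the pairing is thrown away; what is missing is a formal paired test.

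Nor will every participant supply a pair. Research blood is collected where feasible, and section 5.1.1 limits assays to selected participants with adequate samples. Twenty pairs is a ceiling, which is why the figures for 10 pairs are given.

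Finally, the analysis is labelled exploratory. No dose decision, halting rule, or primary or secondary endpoint depends on it, and the Phase II primary endpoint is already a within-participant measure. This limits the severity; it does not supply the missing test.

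**Conclusion.** The point holds as a minor one. Section 10.4.9 names only unpaired comparisons among cohorts, and these cannot show a vaccine effect that the cohorts share: about 5% rejection, against roughly 41% to 95% for a signed-rank test with 20 pairs and 22% to 70% with 10. The cancellation is algebra and does not depend on the assumed values; the power figures do.

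Two stronger conclusions are tempting and not supported. The first is that the planned test has an 81% false-positive rate. That figure needs a 1 SD baseline difference and a comparison of raw post-treatment values. The text does not say whether the percentages are post-treatment values or changes; with changes the rate is about 5%. The second is that a comparison of the two dose levels could never be significant. That is true of the rank sum test at 3 versus 3 but not of the t test, and it applies only if cohorts means dose levels. The 17 versus 20 figures rest on the other meaning, the disease cohorts of section 2.3.2.1, so the two should not be combined.

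**What to change.** In section 10.4.9:
- Make the main PBMC analysis the within-participant change from baseline at named time points (Week 3, and Week 5 in Phase I or Week 4-5 in Phase II), by arm, with the Wilcoxon signed-rank test and the median change with its interval.
- Base it on participants with a baseline and at least one post-dose sample, and report how many pairs there are.
- State what cohort means in this section.
- Keep comparisons between arms, such as vaccine alone versus vaccine plus M7824, on change from baseline, and label them descriptive.

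The cost is a wording change and a little analysis work. No extra blood is needed, since the baseline and on-treatment draws are already scheduled. What is given up is formal significance testing between cohorts, which non-randomised groups of this size could not support well.

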1.2.3 T cell dysfunction in HPV-positive OPSCC

HPV-positive OPSCCs are infiltrated by exhausted and functionally suppressed HPV-specific T cells (19-21). This demonstrates that although an adaptive immune response against one or more HPV antigens develops, these T cells are ineffective at controlling the growth of antigen-expressing tumors. This also suggests that reversing exhaustion in or the suppression of existing HPV-specific T cells may induce HPV antigen-specific anti-tumor immunity. When ligated by programmed death-ligand 1 (PD-L1), signaling through programmed death-receptor 1 (PD-1) on T cells is a significant mechanism of T cell exhaustion (22).

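### The exploratory immune-response rule (10.4.9) ignores the participant's own pre-dose value, so pre-existing HPV-specific T cells can be counted as vaccine responses

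*Combined protocol and SAP*

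**What the plan says.** Section 10.4.9 states that for antigen-specific T cells "a positive immune response is defined by CMI reactivity in" ex vivo stimulation read by flow cytometry (cytokines or CD107), and adds the cut-off: "Antigen-specific peptide challenge assays require a readout of >250 reactive T-cells/million cells above the background". It gives no fold-rise, no difference from the pre-dose sample and no time point. The summary is a responder percentage: "The percentage of subjects with a positive immune response will be evaluated by cohort". On the denominator it says: "A subject will be considered evaluable for immune response if they receive at least one dose of treatment".

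Section 10.4.9 does not define background. The only candidate is in 5.1.1, where "control peptide pools will involve the use of human leukocyte antigen peptide as a negative control". The same section gives the purpose of the work: "Exploratory immunologic studies will be conducted to evaluate the study drug's effect on the immune response before and after treatment". Both study calendars (3.4.1 and 3.4.2) schedule research blood at baseline and after dosing, subject to feasibility.

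On what patients bring with them, section 1.2.3 says that "HPV-positive OPSCCs are infiltrated by exhausted and functionally suppressed HPV-specific T cells". Section 1.2.5 reports that HPV 16-specific T cells expanded in the blood of patients given M7824 without the vaccine.

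**The concern.** The vaccine's rationale (1.2.6) is to induce new T-cell responses, and 1.2.10 separates new from existing antigen-specific cells. Section 1.1.3 lists responses brought about by PRGN-2009 among the exploratory questions. A rule that looks only at the level after stimulation cannot make that separation. It answers whether HPV-specific T cells are present, not whether they appeared or rose after vaccination. A responder percentage on this rule, quoted as evidence of immunogenicity, would mix immunity present before dose 1 with vaccine effect, and the mixing can only raise the figure.

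**Working it through.** No sample size, power or stopping figure in the plan rests on this rule, so there is no stated number to reproduce. The check is of the definition, followed by an illustration of its consequence.

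**Step 1: apply the rule.** Let P be the pre-dose and D the post-dose count per million, each minus background. The written rule is: positive if D > 250. P does not appear. If P = D and both exceed 250, the participant is positive although D − P = 0.

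**Step 2: look for a correction elsewhere.**
- 5.1.1 has a before-and-after aim but no responder definition.
- 10.3 requires adequate pre- and post-treatment samples for the biopsy endpoint, but sets no such condition for the blood assay.
- The t, Kruskal-Wallis and rank-sum tests in 10.4.9 compare percentages of TNF-α or IFN-γ expressing cells "among the different cohorts to determine any significant differences in cell populations". That is a different readout from the responder rule, and not a paired one.
- Reference 53, cited for the cut-off, is listed as a study of a bacterial mutant, so the entry points to no baseline rule and needs correcting.

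Nothing found brings P into the definition.

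**Step 3: size, under assumptions.** Let q be the share already above the cut-off before dose 1 (not in the documents; assumed 10% to 50%) and v the induction rate among the rest (assumed 0 or 20%). If baseline positives stay positive:

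reported rate = q + (1 − q)v; newly induced share = (1 − q)v; excess = q.

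| q | Reported, v = 0 | Of 20 (Arm 2A) | Of 10 (Arm 1B) | Reported, v = 20% | Newly induced, v = 20% |
|---|---|---|---|---|---|
| 10% | 10% | 2 | 1 | 0.10 + 0.90 × 0.20 = 28% | 18% |
| 30% | 30% | 6 | 3 | 0.30 + 0.70 × 0.20 = 44% | 14% |
| 50% | 50% | 10 | 5 | 0.50 + 0.50 × 0.20 = 60% | 10% |

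The planned sizes, 20 and 10, are from 2.3.2.3. Even at q = 10%, the chance of at least one such positive among 20 is 1 − 0.9^20 = 88%.

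**Step 4: where a paired test is usable.** The smallest two-sided exact signed-rank p-value with n pairs (no ties or zero changes) is 2/2^n. For n = 2 (the maximum in Cohort 3) it is 2/4 = 0.5. For n = 3 (each monotherapy dose level in Table 8) it is 2/8 = 0.25. Neither can be informative. Six pairs are the fewest that can go below 0.05 (2/64 = 0.03).

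**The case against.** The strongest reply is that this is an exploratory analysis done when samples allow, that no dose, sample-size or stopping decision uses it, that 10.4.9 also promises a description of response magnitude, and that baseline blood is scheduled, so the before-and-after comparison can be made. All of that stands and limits the importance of the point. It does not repair the responder label, which is a written rule and would be reported as written.

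The reply can add that no document shows anyone above 250 per million in blood before dosing. Section 1.2.3 concerns functionally suppressed cells in tumour, while the assay reads functional cells in blood, and 1.2.5 gives no pre-treatment level. That also stands: the direction of the bias follows from the rule, but its size does not follow from the documents. Reading background as the negative control is likewise an inference from 5.1.1.

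A reader might go further in three ways that the text does not support:
- That the trial cannot show immunogenicity at all. The samples permit a paired comparison; only the label lacks it.
- That treated participants without an assay are counted as non-responders. One dose makes a participant evaluable, and 5.1.1 limits assays to selected participants with enough sample, so the denominator is unclear, but the plan never says how the unassayed are scored.
- That many peptide pools and readouts generate a calculable rate of chance positives. This needs a per-read error rate, independence between reads and an any-visit rule, and the documents give none of them.

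**Conclusion.** The point holds as a defect in an exploratory definition that is worth correcting. As written, immunity present before dose 1 can be reported as a vaccine response. The excess equals the baseline-positive share, provided those participants remain above the cut-off; 2 to 10 of 20 in Arm 2A is an illustration for an assumed 10% to 50%, not an estimate. It would be wrong to infer that the phase II primary endpoint is compromised: that endpoint compares CD3+ infiltration after treatment with the same participant's value before it. In Arm 1B, correcting for baseline would still not separate the vaccine from M7824, since 1.2.5 reports expansion under M7824 without vaccine.

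**What to change.** In 10.4.9:
- State that background is the negative-control peptide well.
- Define a positive response as a post-dose background-subtracted count that exceeds the same participant's pre-dose background-subtracted count, for the same peptide pool and T-cell subset, by more than 250 per million. A difference, unlike a fold-rise, works when the baseline is zero; negative subtracted values can be set to zero so that a low pre-dose reading does not itself create a response.
- Report the baseline-positive rate beside the response rate.
- Base the percentage on participants with a valid baseline and at least one valid post-dose assay, and show the number treated next to it.
- Describe paired changes within each cohort. Use a signed-rank test only where numbers allow, not in Cohort 3 or the dose levels with three participants.

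The cost is mainly wording: no new blood draw is needed. The reported rate will probably be lower, and participants without paired samples leave the denominator. Table 8 already lists 22 participants treated in phase II, so the revised rule should be fixed before the assay data are analysed; otherwise it should be labelled post hoc.
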